6.3.1.2 Handling of additional treatment

Not applicable.

6.3.2 Instruction for prescribing and taking study treatment

- Asciminib should be administered in the fasted state: avoid food for at least 2 hours before the dose is taken and for at least 1 hour after the dose is taken. Water is permitted during this period.
- Asciminib should be taken with approximately 8 ounces (240 mL) of water.
- Asciminib should be swallowed whole and not chewed or crushed.
- If vomiting occurs within the first hour after taking the drug, re-dosing is allowed before the next scheduled dose.
- If the patient on q.d. regimen does not take asciminib within 12 hours after the approximate time of the usual dosing time, that dose should be skipped and treatment should continue with the next daily dose at the prescribed level.
- If the patient on b.i.d. regimen does not take asciminib within 6 hours after the approximate time of the usual dosing time, that dose should be skipped and treatment should continue with the next scheduled dose at the prescribed level.

Table 6-2 Dose and treatment schedule

Study treatments	Pharmaceutical form and route of administration	Target dose/ Daily dose	Use	Tablet Strength	Number of tablets	Regimen
Asciminib	Tablets for oral use	80 mg	Standard Dose	40 mg	1 tablet of 40 mg	b.i.d.
Asciminib	Tablets for oral use	80 mg	Standard Dose	40 mg	2 tablets of 40 mg	q.d.
Asciminib	Tablets for oral use	40 mg	Dose reduction for standard dose b.i.d.	20 mg	1 tablet of 20 mg	b.i.d.
Asciminib	Tablets for oral use	40 mg	Dose reduction for standard dose q.d.	40 mg	1 tablet of 40 mg	q.d.
Asciminib	Tablets for oral use	200 mg	Dose escalation from standard dose*	40 mg	5 tablet of 40 mg	q.d.
Asciminib	Tablets for oral use	80 mg	Dose reduction from 200mg q.d.**	40 mg	2 tablets of 40 mg	q.d.**

Study treatments	Pharmaceutical form and route of administration	Target dose/ Daily dose	Use	Tablet Strength	Number of tablets	Regimen
Asciminib	Tablets for oral use	80 mg	Dose reduction from 200mg q.d.**	40 mg	1 tablet of 40 mg	b.i.d.**

All kits of study treatment will be recorded via the IRT.

* Dose escalation may only occur based on investigators decision after week 48, from week 60 onwards and up to week 120 based on week 108 data.

** Patients on 200 mg q.d. needing a dose de-escalation will revert to 80 mg total daily dose of asciminib and will follow initial dosing schedule, either q.d. or b.i.d., as initially assigned by IRT.

6.4 Participant numbering, treatment assignment, enrollment

6.4.1 Participant numbering

Each participant is identified in the study by a Participant Number (Participant No.), that is assigned within EDC system when the participant is screened and is retained for the participant throughout his/her participation in the trial. A new Participant No. will be assigned at every subsequent enrollment if the participant is re-screened. The Participant No. consists of the Center Number (Center No.) (as assigned by Novartis to the investigative site) with a sequential participant number suffixed to it, so that each participant's participation is numbered uniquely across the entire database. Upon signing the informed consent form, the participant is assigned to the next sequential Participant No. available.

A new ICF will need to be signed if the investigator chooses to re-screen the participant after a participant has screen failed, and the participant will be assigned a new Participant No.

The investigator or designated staff will contact the IRT and provide the requested identifying information for the patient to register them into the IRT. Once assigned, the Subject No. must not be reused for any other subject and the Subject No. for that individual must not be changed. If the patient fails to be enrolled or start treatment for any reason, (i.e if a patient is screen failed) the reason will be entered into the Screening Disposition page. IRT must be notified by investigator or his/her delegate within 2 days of visit that the patient was enrolled or not.

6.4.2 Treatment assignment

One to one randomization to asciminib 40 mg b.i.d. and asciminib 80 mg q.d. will be performed by IRT for all patients (who were treated with two or more TKIs and who were either resistant or intolerant to the last treatment; and also on the additional patients intolerant only to their last TKI treatment and in MMR at baseline) upon eligibility confirmation. B.i.d. or q.d. dosing allocated at trial start must be maintained for patients who remain at standard dose, or need to de-escalate after increase to 200 mg q.d.

6.4.2.1 Replacement policy

Patients that drop out of the study for any reason after having taken the first tablet of study medication will not be replaced.

6.5 Treatment blinding

Not applicable.

6.6 Dose escalation and dose modification

The standard dose for all patients in this study is asciminib 40 mg b.i.d. or 80 mg q.d. For patients not achieving MMR at 48 weeks or losing the response after the week 48 assessment up to week 108, a dose escalation to 200 mg q.d. may be considered per investigator decision.

6.6.1 Dose escalation guidelines

6.6.1.1 Starting dose

The starting dose for patients will either be asciminib 40 mg b.i.d. or 80 mg q.d. as assigned by IRT upon eligibility confirmation. The q.d. or b.i.d. regimen allocated at randomization must be maintained throughout the study for patients who do not need to escalate dose, or need to de-escalate from 200 mg q.d.

6.6.2 Dose escalation

For patients not in MMR at 48 weeks or losing the response after the week 48 assessments up to week 108, a dose escalation to 200 mg q.d. may be considered for patients on 40 mg b.i.d. or 80 mg q.d., if in the investigator's opinion the patient may benefit from the escalation. In addition, there must not be any grade 3 or 4 toxicity while on therapy, or persistent grade 2 toxicity, possibly related to asciminib and unresponsive to optimal management.

Patients with dose reduction to 40 mg due to side effects may receive a dose escalation to 200 mg daily if the event requiring the dose reduction has disappeared and the patient has been treated at least 3 months on the standard dose of 80 mg.

CCI [REDACTED] will be performed in patients not reaching MMR at 48 weeks or patients losing the response after the week 48 assessments up to week 108, and for whom a dose escalation might benefit the patient, to identify potential BCR-ABL mutations that could confer resistance to asciminib. With the limited information on mutations no general treatment recommendations can be given for individual mutations.

Dose escalation may be performed at week 60 for patients not in MMR at week 48. For patients losing the response after week 48 up to week 108, dose escalation may be performed up to week 120 after confirmed loss of MMR in 2 consecutive tests and CCI [REDACTED] results are available.

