9.1 Discontinuation from study treatment and from study

9.1.1 Discontinuation from study treatment

Discontinuation of study treatment for a participant occurs when study treatment is permanently stopped for any reason (earlier than the planned completion of study drug administration) and can be initiated by either the participant or the investigator.

The investigator must discontinue study treatment for a given participant if, he/she believes that continuation would negatively impact the participant's well-being.

Study treatment must be discontinued under the following circumstances:

- Participant/guardian decision
- Pregnancy
- Use of prohibited treatment. Refer to [Section 6.2.2](#).
- Any situation in which continued study participation might result in a safety risk to the participant
- In the case of certain adverse events and re-occurrence of adverse events (see [Table 6-4](#))
- Major Protocol Deviation, or any other protocol deviation that results in a significant risk to the patient's safety.

In addition to the general discontinuation criteria, the following study specific criteria will also require discontinuation of study treatment:

- In the event of treatment failure the patient should be discontinued from the study treatment. The ELN criteria 2020 do not make provisions for treatment failure in 3rd line however they define that a level of BCR-ABL1 > 1% IS and failure to achieve CCyR is not sufficient for optimal survival. The following events will constitute 'treatment failure':
 - BCR-ABL1 >1% IS at 48 weeks after initiation of therapy or no complete cytogenetic response at 48 weeks.

- Patients fulfilling treatment failure criteria above but without alternative treatment options may however be continued on study drug if in the investigators opinion they are obtaining benefit from the drug. Patients with BCR-ABL 1 greater than 10% after 48 weeks of treatment or patients with signs of progression to AP and BC must however be discontinued.
- Patients with newly emerging T315I mutation and lack or loss of response. While asciminib has known activity against CML with additional T315I mutation, the recommended dose of 200 mg BID for the treatment of T315I is not in use in the study. In case a patient demonstrates a new T315I mutation on asciminib, patients should not continue in the study.

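### Protocol 6.6.2 permits escalation to 200 mg q.d. without an upper BCR-ABL1 limit, while 9.1.1 stops some of the same Week-48 patients; neither section says which prevails, and the SAP inherits the conflict

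*Protocol*

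**What the plan says.** **Escalation (Protocol 6.6.2).** "Dose escalation may be performed at week 60 for patients not in MMR at week 48". The decision is open "if in the investigator's opinion the patient may benefit from the escalation", and "there must not be any grade 3 or 4 toxicity while on therapy, or persistent grade 2 toxicity, possibly related to asciminib". BCR-ABL1 and mutation results must be available first, and a patient previously reduced to 40 mg must meet further conditions. The same response trigger appears in the protocol summary and in sections 3, 4.2, 6.1 and 6.6. A second trigger is loss of response after Week 48, up to Week 108. The footnote to Table 6-2 gives only timing and investigator decision, with no MMR condition.

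**Stopping (Protocol 9.1.1).** The list opens with the words "the following study specific criteria will also require discontinuation of study treatment". It continues: "In the event of treatment failure the patient should be discontinued from the study treatment". Failure is defined as "BCR-ABL1 >1% IS at 48 weeks after initiation of therapy or no complete cytogenetic response at 48 weeks". There is one exception: "Patients fulfilling treatment failure criteria above but without alternative treatment options may however be continued on study drug", provided the investigator sees benefit. A limit on that exception follows: patients with BCR-ABL1 "greater than 10% after 48 weeks of treatment or patients with signs of progression to AP and BC must however be discontinued".

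**SAP.** Section 1.1 repeats the escalation rule, and 5.4.4 repeats the stopping rule with its exception. Section 5.4.4 also counts confirmed loss of MMR as treatment failure. Section 2.1.1 removes efficacy assessments made after treatment failure from every efficacy analysis except OS and PFS. Section 2.5.6 plans an MMR rate with a 95% confidence interval at Weeks 96 and 144 in escalated subjects.

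**The concern.** Not being in MMR means BCR-ABL1 above 0.1%. That range contains the whole region in which 9.1.1 calls for stopping. An investigator working from the escalation section meets no ceiling and no pointer to 9.1.1; one working from 9.1.1 finds no mention of escalation. Two sites following the protocol in good faith could therefore give the same kind of patient opposite management at Week 60: a dose increase at one, withdrawal of drug at the other.

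For patients whom 9.1.1 says must stop, this is a safety matter. For the analysis, it makes the composition of the escalated group depend on which section a site followed. It also affects the Week 72, 96 and 144 response rates, because SAP 2.6.2 counts patients who discontinued before a time point as non-responders.

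**Working it through.** **1. The plan's own figures.** Inputs from Protocol 12.8.1: n = 156, null rate 0.23, alternative 0.33, one-sided 0.025, exact test. The smallest r with P(X ≥ r | 156, 0.23) ≤ 0.025 is r = 47, where the tail is 0.0241. P(X ≥ 47 | 156, 0.33) = 0.801, which agrees with the stated 80%. The source of the null also reproduces: 6/54 = 11.1%, Clopper-Pearson 4.2% to 22.6%. None of this involves escalation, which starts at Week 60, after the endpoint is read.

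**2. The two sections side by side, by Week-48 result** (6.6.2 benefit and toxicity conditions assumed met):

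| Week-48 status | 6.6.2 | 9.1.1 | Result |
|---|---|---|---|
| >0.1-1%, CCyR | may escalate | no stop on response | compatible |
| >1-10%, or no CCyR at ≤10%; no alternative, benefiting | may escalate | may continue | compatible |
| >1-10%, or no CCyR at ≤10%; alternative available | may escalate | should stop | conflict |
| >10%, or signs of AP/BC | may escalate | must stop | conflict |

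The availability of an alternative treatment decides the middle rows, yet it appears nowhere in the escalation conditions.

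**3. How many patients.** Non-responders at the planning rate: 156 × (1 − 0.33) = 104.5, about 105. At the null rate: 156 × 0.77 = 120.1. Both are upper bounds on those who could be considered for escalation at Week 60. They include patients who discontinued earlier (non-responders under SAP 2.5.3) and most patients with a missing Week-48 PCR (SAP 2.5.4).

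The share above 1% or without CCyR is not given. As assumptions:

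- 10%: 104.5 × 0.10 = 10
- 25%: 104.5 × 0.25 = 26
- 50%: 104.5 × 0.50 = 52
- 75%: 104.5 × 0.75 = 78

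The base may be much smaller. Purely as an illustration, take the 37.6% asciminib discontinuation quoted in Protocol 1.1 from the earlier phase III trial (different population and follow-up), and treat all of it as occurring before Week 48. Then 156 × 0.376 = 58.7 and 104.5 − 58.7 = 45.9. The 10% and 75% shares become about 5 and 34. In every case these count treatment failures. Those in conflict are fewer, because failures within the 9.1.1 exception drop out.

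**4. The SAP chain.** Take a patient at 5% at Week 48 who is escalated at Week 60.

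- SAP 5.4.4 makes the patient a treatment failure at Week 48.
- SAP 2.1.1 then excludes the later PCR results.
- SAP 2.5.6 nevertheless includes the patient in the Week 96 and 144 escalator rate.
- Under SAP 2.6.2, a patient with no available assessment at a time point is a non-responder.

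Patients escalated after confirmed loss of MMR meet the same sequence. Read literally, among patients escalated for not being in MMR at Week 48, only those at >0.1-1% with CCyR and no other failure criterion could contribute a later response.

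**The case against.** The strongest reply is that the texts can be read together. Escalation presupposes a patient still on 40 mg b.i.d. or 80 mg q.d., and a permission does not cancel a mandatory stop. A patient stopped on the Week-48 result is not on drug at Week 60. That is a tenable reading above 10%, but no visible text states it. It cannot settle the group at or below 10%, where the operative verb is should and the exception depends on a condition that 6.6.2 omits. The rationale in Protocol 4.2 and 4.5 also describes a positive balance at 200 mg for patients who miss MMR, without a ceiling.

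Three other points stand and limit the finding. The protocol says repeatedly that this population has few remaining options, so the exception may cover a substantial share of failures. The escalator analysis is supplementary and descriptive. Figure 3-1 is not reproduced in the text available, so the absence of a limit can be asserted only for the visible text.

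A reader might infer that any patient not in MMR may escalate, or that everyone outside the >0.1-1% band with CCyR is in conflict. Neither holds: the first ignores the benefit and toxicity conditions, the second the 9.1.1 exception.

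**Conclusion.** This is an internal inconsistency, wrong as written. It applies to patients above 10% or with signs of AP/BC, and to Week-48 treatment failures at or below 10% who have an alternative treatment. For all other patients meeting the escalation conditions, the two sections are compatible on Week-48 response.

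Its size is not derivable. About 105 of 156 is a ceiling on the pool, resting on the 33% planning rate, and should not be read as the number affected. Describing the affected patients as many would go beyond the documents.

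It would also be wrong to infer a threat to the primary result: the Week-48 endpoint, its error rate and the sample size are untouched. What is exposed is patient management after Week 48, the later response rates and the interpretability of the escalator analysis. For that analysis, the SAP adds its own conflict between 2.1.1, 2.5.6 and 5.4.4. Which clinical rule should hold is for the sponsor.

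**What to change.** **Protocol.** Reconcile 6.1, 6.6.2 and the Table 6-2 footnote with 9.1.1, and cross-refer them. State which provision prevails by Week-48 BCR-ABL1 band (>0.1-1%, >1-10%, >10%), CCyR status and availability of alternatives. A small table would do this, but explicit precedence wording covering the same cases would serve. The sponsor decides the content.

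**SAP.** Reconcile 2.1.1, 2.5.6 and 5.4.4, stating explicitly whether assessments after treatment failure count in the Week 96 and 144 escalator rates. Then tabulate escalators by Week-48 BCR-ABL1 band. The tabulation alone would not be enough, because under 2.1.1 the later results of escalated failures would still be excluded.

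**Cost.** A protocol clarification or amendment and a SAP edit; no new data.

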6.6.3 Dose modifications

For participants who do not tolerate the protocol-specified dosing schedule, dose interruptions, and/or reductions are either recommended or mandated in order to allow participants to continue the study treatment.

Table 6-3 Dose reduction schedule

*Dose reduction			
		Starting dose level 0	Dose level – 1
Asciminib	CML-CP	40 mg b.i.d. (total daily dose 80 mg)	20 mg b.i.d. (total daily dose 40 mg)
	CML-CP	80 mg q.d. (total daily dose 80 mg)	40 mg q.d. (total daily dose 40 mg)
	CML-CP	200 mg q.d. (total daily dose 200 mg)	80 mg q.d. or 40 mg b.i.d. (total daily dose 80 mg)**
*Dose reduction should be based on the worst toxicity demonstrated at the last dose.			
**Patients on 200 mg q.d. needing a dose de-escalation will revert to 80 mg total daily dose of asciminib, according to pre-escalation dosing schedule (q.d. or b.i.d. regimen assigned at enrollment).			
Asciminib dose reduction below total daily dose of 40 mg (20 mg b.i.d. or 40 mg q.d.) is not allowed. 20 mg tablets will be dispensed to patients having 20 mg b.i.d. regimen in the instance of dose reduction.			

These dose modifications, in addition to permanent treatment discontinuations, are summarized in (Table 6-4). Deviations to mandatory dose interruptions and/or reductions are not allowed.

These dose changes must be recorded on the appropriate CRF.

A patient must discontinue treatment with asciminib if, after treatment is resumed at a lower dose level, the toxicity recurs with the same or worse severity, except for recurrence of cytopenias (Table 6-4). If a patient requires a dose interruption of > 28 days for each non-hematologic toxicity, then the patient must be discontinued from the study treatment. If a hematologic toxicity (cytopenia Grade 3 or 4) last for more than 42 days without recovery to at least a Grade 2, despite asciminib interruption and adequate management (including hematopoietic growth factors), then the patient must be discontinued from study treatment.

Table 6-4 Criteria for dose reduction / interruption / discontinuation and re-initiation of treatment for adverse drug reactions

Dose modifications for asciminib	
Please note that if a patient requires a dose interruption of > 28 days for any toxicity, and > 42 days for hematologic toxicity, then the patient should be discontinued from study treatment	
Worst toxicity CTCAE Version 5.0	Asciminib
Investigations (hematologic): If a hematologic toxicity (cytopenia grade 3 or 4) lasts for more than 42 days without recovery to at least grade 2, despite asciminib interruption and adequate management (including hematopoietic growth factors), then the patient should be discontinued from study treatment.	
Neutropenia (ANC)	
Grade 1 (ANC < LLN – 1.5 x 10 ⁹ /L)	Recommendation: Maintain dose level
Grade 2 (ANC < 1.5 – 1.0 x 10 ⁹ /L)	Recommendation: Maintain dose level
Grade 3 (ANC < 1.0 – 0.5 x 10 ⁹ /L)	Mandatory: Hold dose until resolved to grade ≤ 2 (recheck CBC 2x/week), then: if resolved in ≤ 14 days, then maintain dose level If resolved in > 14 days, then reduce dose ↓ 1 dose level
Grade 4 (ANC < 0.5 x 10 ⁹ /L)	Mandatory: Hold dose until resolved to grade ≤ 2, (recheck CBC 2x/week), then: if resolved in ≤ 14 days, then maintain dose level if resolved in > 14 days, then reduce dose ↓ 1 dose level

Dose modifications for asciminib	
Please note that if a patient requires a dose interruption of > 28 days for any toxicity, and > 42 days for hematologic toxicity, then the patient should be discontinued from study treatment	
Worst toxicity CTCAE Version 5.0	Asciminib
Febrile neutropenia (ANC < 1.0 x 10 ⁹ /L, fever ≥ 38.5°C)	Mandatory: Hold dose until resolved, then reduce dose ↓ 1 dose level
Thrombocytopenia	
Grade 1 (PLT < LLN – 75 X 10 ⁹ /L)	Recommendation: Maintain dose level
Grade 2 (PLT < 75 - 50 x 10 ⁹ /L)	Recommendation: Maintain dose level
Grade 3 (PLT < 50 - 25 x 10 ⁹ /L)	Mandatory: Hold dose until resolved to grade ≤ 2 (recheck CBC 2x/week), then: if resolved in ≤ 14 days, then maintain dose level if resolved in > 14 days, then reduce dose ↓ 1 dose level
Grade 4 (PLT < 25 x 10 ⁹ /L)	Mandatory: Hold dose until resolved to grade ≤ 2 (recheck CBC 2x/week), then: if resolved in ≤ 14 days, then maintain dose level if resolved in > 14 days, then reduce dose ↓ 1 dose level
Recurrence of any cytopenia	Recommendation: Hold dose until resolved to grade ≤ 2, then maintain current dose level For recurrent Grade 3/4 cytopenia, please refer to above guidelines for neutropenia and thrombocytopenia; no further dose reduction is allowed for already reduced dose.
Non-hematologic adverse reactions except where further specified in individual sections	
Grade 1	Recommendation: Maintain dose level
Grade 2	Recommendation: Hold dose until resolved to grade ≤ 1, then maintain dose level
Grade 3	Mandatory: Hold dose until resolved to grade ≤ 1, then reduce dose ↓ 1 dose level
Grade 4	Mandatory: Permanently discontinue patient from treatment
Investigations (renal)	
Serum creatinine	
Grade 1 (> ULN - 1.5 x ULN)	Recommendation: Maintain dose level
Grade 2 (> 1.5 - 3.0 x ULN)	Recommendation: Hold dose until resolved to grade ≤ 1 or baseline, then maintain dose level
Grade 3 (> 3.0 - 6.0 x ULN)	Mandatory: Permanently discontinue patient from treatment
Grade 4 (> 6.0 x ULN)	Mandatory: Permanently discontinue patient from treatment
Investigations (hepatic)	
Isolated total bilirubin elevation	
> ULN – 1.5 x ULN, if baseline was normal	Recommendation: Maintain dose level
> 1.5 - 3.0 x ULN if baseline was normal	Recommendation: Maintain dose. Repeat Liver Function Tests (LFT) within 48-72 hours then monitor LFTs ^b weekly, or more frequently if clinically indicated, until resolved to ≤ 1.5 x ULN or baseline: if resolved in ≤ 14 days, then maintain dose level if resolved in > 14 days, then reduce dose ↓ 1 dose level
> 3.0 - 10.0 x ULN (irrespective of the baseline levels) *	Mandatory: Hold dose. Repeat LFTs within 48-72 hours then monitor LFTs ^b weekly, or more frequently if clinically indicated, until resolved to ≤ 1.5 x ULN or baseline: if resolved in ≤ 14 days, then reduce dose ↓ 1 dose level if resolved in > 14 days, then discontinue patient from treatment.

Dose modifications for asciminib	
Please note that if a patient requires a dose interruption of > 28 days for any toxicity, and > 42 days for hematologic toxicity, then the patient should be discontinued from study treatment	
Worst toxicity CTCAE Version 5.0	Asciminib
	The patient should be monitored weekly (including LFTs ^b), or more frequently if clinically indicated, until total bilirubin level has resolved to baseline or has stabilized over 4 weeks
> 10.0 x ULN (irrespective of the baseline levels) *	See footnote**** - otherwise discontinue study treatment The patient should be monitored weekly (including LFTs ^b), or more frequently if clinically indicated, until total bilirubin level has resolved to baseline or has stabilized over 4 weeks
Isolated AST or Alanine Aminotransferase (ALT) elevation	
If normal at baseline:	
> ULN - 3.0 x ULN	Recommendation: Maintain dose level Repeat liver tests within 48- 72 hours, then monitor weekly until recovery to ≤Grade 1 or to baseline
> 3.0 - 5.0 x ULN	Recommendation: Maintain dose level. Repeat LFTs ^b as soon as possible, preferably within 48-72 hours from awareness of the abnormal results; if abnormal lab values are confirmed upon the repeat test, then monitor LFTs ^b weekly, or more frequently if clinically indicated, until resolved to ≤ 3.0 x ULN
> 5.0 - 10.0 x ULN	Mandatory: Omit dose. Repeat LFTs ^b as soon as possible, preferably within 48-72 hours from awareness of the abnormal results; monitor LFTs ^b weekly, or more frequently if clinically indicated, until resolved to ≤ 3.0 x ULN. Then: If resolved in ≤ 14 days, resume at prior dose level If resolved in > 14 days, resume with reduced dose ↓ 1 dose level
> 10.0 - 20.0 x ULN	Mandatory: Omit dose. Repeat LFTs ^b as soon as possible, preferably within 48-72 hours from awareness of the abnormal results; monitor LFTs ^b weekly, or more frequently if clinically indicated, until resolved to ≤ baseline. Then resume with reduced dose ↓ 1 dose level
> 20.0 x ULN	Mandatory: Permanently discontinue
If elevated at baseline:	
> Baseline - 3.0 x Baseline AND ≤ 5 x ULN	Recommendation: Maintain dose level
> 3.0 x Baseline AND > 5.0 x ULN (duration less than 2 weeks)	Recommendation: Maintain dose level. Repeat LFTs ^b as soon as possible, preferably within 48-72 hours from awareness of the abnormal results; if abnormal lab values are confirmed upon the repeat test, then monitor LFTs ^b weekly, or more frequently if clinically indicated, until resolved to ≤ ULN or baseline
> 3.0 x Baseline AND > 5.0 x ULN (duration more than 2 weeks):	Mandatory: Omit dose. Repeat LFTs ^b as soon as possible, preferably within 48-72 hours from awareness of the abnormal results; if abnormal lab values are confirmed upon the repeat test, then monitor LFTs ^b weekly, or more frequently if clinically indicated, until resolved to ≤ ULN or baseline. If resolved, resume with reduced ↓ 1 dose level.
> 5.0 x Baseline AND > 8.0 x ULN (irrespective of the duration):	Mandatory: Omit dose. Repeat LFTs ^b as soon as possible, preferably within 48-72 hours from awareness of the abnormal results; if abnormal lab values are confirmed upon the repeat test, then monitor LFTs ^b weekly, or more frequently if clinically indicated, until resolved to ≤ ULN or baseline. If resolved, resume with reduced ↓ 1 dose level.
> 20.0 x ULN	Permanently discontinue
Combined ^c elevations of AST or ALT and total bilirubin	


Dose modifications for asciminib Please note that if a patient requires a dose interruption of > 28 days for any toxicity, and > 42 days for hematologic toxicity, then the patient should be discontinued from study treatment
	

Worst toxicity CTCAE Version 5.0
	
Asciminib

For patients with normal baseline ALT and AST and total bilirubin value:
 
AST or ALT > 3.0 x ULN combined with total bilirubin > 2.0 x ULN without evidence of cholestasis^d
 
For patients with elevated baseline AST or ALT or total bilirubin value [AST or ALT > 3 x baseline OR [AST or ALT > 8.0 x ULN], whichever is lower combined with total bilirubin > 2 x baseline AND > 2.0 x ULN
 
Note: For participants with Gilbert's syndrome, at least 2-fold increase in direct bilirubin
	
Mandatory: Hold dose
 
Repeat liver tests as soon as possible, preferably within 48 hours from awareness of the abnormal results, then with weekly monitoring of LFTs^b, or more frequently if clinically indicated, until AST, ALT, or bilirubin have resolved to baseline or stabilization over 4 weeks. Please refer to Section 6.6.4.1 for additional follow-up evaluations as applicable.
 
If DILI confirmed: permanently discontinue patient from study drug treatment
 
If not DILI – interrupt treatment. Treat identified cause according to institutional guidelines. If resolved, then reduce dose ↓ 1 dose level, if cause is treatment related.

Investigation (metabolic)
	

Amylase and/or lipase elevation
	

Grade 1: > ULN - 1.5 x ULN
	
Recommendation: Maintain dose level, measure 2x per week

Grade 2: > 1.5 - 2.0 x ULN; >2.0 - 5.0 x ULN and asymptomatic
	
Recommendation: Maintain dose level, measure 2x per week

Grade 3: > 2.0 - 5.0 x ULN with signs or symptoms; >5.0 x ULN and asymptomatic
	
Mandatory: Hold dose until resolved to Grade ≤ 1 or baseline, then: If resolved in ≤ 7 days, then reduce dose ↓ 1 dose level If resolved in > 7 days, then discontinue treatment and obtain appropriate imaging (i.e., MRI, CT scan, or ultrasound) **

Grade 4: > 5.0 x ULN and with signs or symptoms
	
Mandatory: Permanently discontinue patient from treatment. Obtain appropriate imaging (i.e., MRI, CT scan, or ultrasound) **

Vascular disorders
	

Hypertension
	

Systolic BP 140-159 mm Hg or Diastolic BP 90-99 mm Hg
	
Mandatory: If recurrent or persistent (≥24 hrs), or if symptomatic increase by >20 mm Hg (diastolic) or to >140/90 mm Hg; monotherapy anti-hypertensive treatment indicated; Maintain asciminib dose level, with regular monitoring of blood pressure.

Systolic BP ≥160 mm Hg or Diastolic BP ≥100 mm Hg
	
Medical intervention indicated: Initiate antihypertensive therapy (if not currently being treated with antihypertensive). If already taking anti-hypertensive drugs; intensive treatment with increased dose of existing anti-hypertensive/ more than one anti-hypertensive drugs than previously used Hold asciminib dose until resolved to grade ≤ 2, then reduce dose ↓ 1 dose level

CTCAE Grade 4
	
Mandatory: Permanently discontinue patient from treatment

Gastrointestinal
	

Pancreatitis
	

Dose modifications for asciminib	
Please note that if a patient requires a dose interruption of > 28 days for any toxicity, and > 42 days for hematologic toxicity, then the patient should be discontinued from study treatment	
Worst toxicity CTCAE Version 5.0	Asciminib
Grade 2 (radiologic findings for pancreatitis as per CTCAE v5.0, for increased enzymes please see table for asymptomatic amylase and/or lipase elevation)	Mandatory: If asymptomatic radiologic pancreatitis, hold treatment until recovery of the radiologic findings. If treatment delay is ≤ 21 days, then reduce dose ↓ 1 dose level. If treatment delay > 21 days, discontinue treatment and keep monitoring with appropriate imaging (i.e., MRI, CT scan, or ultrasound) **
Grade ≥ 3	Mandatory: Permanently discontinue patient from treatment. Obtain appropriate imaging (i.e., MRI, CT scan, or ultrasound)
Diarrhea***	
Grade 1	Recommendation: Maintain dose level but initiate anti-diarrhea treatment
Grade 2	Recommendation: Hold dose until resolved to grade ≤ 1, then maintain dose level If diarrhea returns as grade ≥ 2, hold dose until resolved to grade ≤ 1, then reduce dose ↓ 1 dose level
Grade 3	Recommendation: Hold dose and discontinue patient from treatment
Grade 4	Mandatory: Permanently discontinue patient from treatment
Skin and subcutaneous tissue disorders	
Rash/photosensitivity	
Grade 1	Recommendation: Maintain dose level. Consider initiating appropriate skin toxicity therapy (such as antihistamines, topical corticosteroids and low-dose systemic corticosteroids)
Grade 2	Recommendation: Maintain dose level, but initiate/intensify appropriate skin toxicity therapy (such as antihistamines, topical corticosteroids and low-dose systemic corticosteroids)
Grade 3, despite skin toxicity therapy	Recommendation: Hold dose until resolved to grade ≤ 1, then: If resolved in ≤ 7 days, reduce dose ↓ 1 dose level If resolved in > 7 days (despite appropriate skin toxicity therapy), discontinue patient from treatment
Grade 4, despite skin toxicity therapy	Mandatory: Permanently discontinue patient from treatment
General disorders and administration site conditions	
Fatigue/Asthenia	
Grade 1 or 2	Recommendation: Maintain dose level
Grade 3	Recommendation: Hold dose until resolved to grade ≤ 1, then: If resolved in ≤ 7 days, maintain dose level If resolved in > 7 days, reduce dose ↓ 1 dose level

All dose modifications should be based on the worst preceding toxicity.
 
^a Common Terminology Criteria for Adverse Events (CTCAE Version 5.0).
 
^b Core LFTs consist of ALT, AST, total bilirubin (fractionated [direct and indirect], if total bilirubin > 2.0 x ULN), and alkaline phosphatase (ALP) (fractionated [quantification of isoforms], if ALP > 2.0 x ULN).
 
^c “Combined” defined as total bilirubin increase to the defined threshold concurrently with ALT/AST increase to the defined threshold.
 
If combined elevations of AST or ALT and total bilirubin do not meet the defined thresholds, please follow the instructions for isolated elevation of total bilirubin and isolated elevation of AST/ALT, and take a conservative action based on the degree of the elevations (e.g. discontinue treatment at the situation when hold dose is needed for one parameter and discontinue treatment is required for another parameter). After all elevations resolve to the defined thresholds that allow treatment re-initiation, re-start the treatment either at the same dose or at one dose lower if meeting a criterion for dose reduction.
	

Dose modifications for asciminib	
Please note that if a patient requires a dose interruption of > 28 days for any toxicity, and > 42 days for hematologic toxicity, then the patient should be discontinued from study treatment	
Worst toxicity CTCAE Version 5.0	Asciminib

^d “Cholestasis” defined as ALP elevation (> 2.0 x ULN and R value < 2) in patients
 
Note: The R value is calculated by dividing the ALT by the ALP, using multiples of the ULN for both values. It denotes whether the relative pattern of ALT and/or ALP elevation is due to cholestatic (R ≤ 2), hepatocellular (R ≥ 5), or mixed (R >2 and < 5) liver injury.
 
* Note: If total bilirubin > 3.0 x ULN is due to the indirect (non-conjugated) component only, and hemolysis as the etiology has been ruled out as per institutional guidelines (e.g., review of peripheral blood smear and haptoglobin determination), then ↓ 1 dose level and continue treatment at the discretion of the investigator.
 
** Note: A CT scan or other imaging study to assess the pancreas, liver, and gallbladder should be performed within 1 week of the first occurrence of any grade ≥ 3 amylase and/or lipase elevation. If asymptomatic grade 3 elevations of lipase and/or amylase occur again at the reduced dose, patients will be discontinued permanently from study treatment. If asymptomatic grade 2 re-occur at reduce dose, closed monitoring of lipase and amylase will be required.
 
*** Note: Antidiarrheal medication is recommended at the first sign of abdominal cramping, loose stools, or overt diarrhea.
 
**** Note: An isolated bilirubin elevation is not typical for drug-induced liver injury. Bilirubin can be elevated either as part of a “Hy’s law” constellation with a preceding elevation of ALT/AST, or as part of a cholestatic reaction with simultaneous elevation of other cholestatic parameters (ALP, GGT). Isolated bilirubin can be seen in conjunction with drugs that inhibit bilirubin conjugation or excretion, but both scenarios do not typically represent liver injury. Alternative causes of bilirubin elevation should therefore, be ruled out before basing dose modification decisions on bilirubin values alone.
	

